9 STATISTICAL METHODS

The study is a prospective, open-label, multicenter, dose escalation, and safety with PK and dosimetry study of injected Tc 99m tilmanocept in the detection of and assessment of localization to skeletal joints in subjects with and without active RA by SPECT and SPECT/CT imaging. The dose escalation portion of the study is a modified 3+3 design with no dose de-escalation as described in [Chevret \(2006\)](#). The statistical objective of the study is to determine the maximum tolerated dose (MTD) of Tc 99m tilmanocept and to compare the capabilities of Tc99m tilmanocept between subjects with and without RA.

A study center is defined as a treatment administration site or group of treatment administration sites under the control and supervision the same Primary Investigator.

9.1 Randomization Methods

The study is not randomized.

9.2 Safety Variables

The primary variable for this study is whether a subject observes any pharmacologic activity or an ADR during their enrollment in the trial. This is a safety endpoint. The pharmacologic activity or ADR must be observed after the dose of Tc99m tilmanocept is administered.

9.3 Efficacy Variables

The efficacy variables for this study are as follows:

- Nuclear medicine specialist qualitative determination of presence/absence of radiotracer uptake (i.e., Tc 99m tilmanocept localization positive/negative) relative to background from SPECT imaging results for each DAS28 joint location for each subject (deemed the “gold standard” result, 28 joint locations per subject)
 - Clinically identified presence/absence of RA using the DAS28 instrument (28 joint locations per subject)
- Quantitative planar imaging intensity of radiotracer uptake for each joint location

A location/joint would be considered clinically identified as RA positive if it is either swollen or tender as measured by the DAS28 instrument. The presence of radiotracer uptake relative to background as determined by the nuclear medicine specialist at a location would indicate the location is RA positive.

The efficacy endpoints for this study are as follows:

- Per subject localization rate of Tc 99m tilmanocept by SPECT imaging
- Per joint location clinically RA-identified joint localization rate of Tc 99m tilmanocept by SPECT imaging

- Concordance of Tc 99m localization with anatomical areas of active RA defined by clinical symptomology.
- Localization intensity for each clinically RA-defined joint (as determined by quantitative SPECT gamma counts)
- Per subject localization rate of Tc 99m tilmanocept in areas other than RA-positive joints by SPECT imaging
- The following PK parameters will be calculated for each subject, whenever possible, using Tc 99m tilmanocept total radioactivity in whole blood and urine: maximum observed concentration (C_{max}), time to C_{max} (t_{max}), area under the concentration-time curve (AUC) from Hour 0 to the last measureable concentration (AUC_{0-t}), AUC extrapolated to infinity ($AUC_{0-\infty}$), apparent terminal elimination rate constant (λ_z), and apparent terminal elimination half-life ($t_{1/2}$).
- Radiation dosimetry of Tc 99m tilmanocept will include radiation doses per organ ($\mu\text{Gy}/\text{MBq}$), organs receiving the highest organ dose (HT), effective doses per organ ($\mu\text{Sv}/\text{MBq}$), mean effective dose ($\mu\text{Sv}/\text{MBq}$), effective dose resulting from a diagnostic dose $\pm 20\%$. Dosimetry will be based on target organ image counts and modeling per OLINDA/EXM® 2.0 software.

Per subject localization of Tc99m by SPECT imaging is defined as the illumination of at least one site relative to background in a subject as determined by the nuclear medicine specialist.

Per joint location RA-identified localization rate is the number of joint locations that are clinically RA positive and SPECT illuminated divided by the total number of joints.

Per joint location concordance of Tc99m localization to clinically positive RA joints is the number of joint locations that are clinically RA positive and SPECT illuminated divided by the number of clinically RA positive joints.

Per subject localization rate of Tc99m by SPECT imaging in areas other than RA-positive joints is defined as the illumination of at least one joint location relative to background that is clinically RA negative in a subject divided by the number of subjects.

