ICH	International Conference on Harmonization
%ID _{SN}	percentage of Injected Dose in the Sentinel Node
ILM	intraoperative lymphatic mapping
IRB	Institutional Review Board
ISF	investigator site file
ITD	intent-to-diagnose population
IV	intravenous
kDa	kiloDalton (molecular weight designation)
mCi	milliCurie (37x10 ⁶ becquerels; 37megabecquerels)

MedDRA	Medical Dictionary for Regulatory Activities
MTD	maximum tolerated dose
NOAEL	no-observed adverse-effect level
NSAIDS	Nonsteroidal anti-inflammatory drug
OA	osteoarthritis
OLINDA/EXM®	Organ Level Internal Dose Assessment/EXponential Modeling
PI	principal investigator
PK	Pharmacokinetics
PP	per protocol
RA	Rheumatoid arthritis
RBC	red blood cells
RF	Rheumatoid Factor
RPK	Radiopharmacokinetic
SAE	serious adverse event
SAP	statistical analysis plan
SCC	squamous cell carcinoma
SD	study day
SJC	swollen joint count
SLN	sentinel lymph node
SLNB	sentinel lymph node biopsy
SPECT	single photon emission computed tomography
SUSARs	Suspected, Unexpected, Serious Adverse Reactions
$t_{1/2}$	apparent terminal elimination half life
t_{max}	time to C_{max}
Tc 99m	technetium-99m metastable isotope; γ -emitting ($t_{1/2} = 6.02$ h)
TcSC	Tc 99m sulfur colloid
Tilmanocept	DTPA Mannosyl Dextran (the US Adopted Name for the drug substance of Lymphoseek)
TJC	tender joint count
TMF	trial master file

TNF α	Tumor necrosis factor alpha
ULN	upper limit of normal
US	United States
VAS	visual analog scale
VBD	vital blue dye
WBC	white blood cell
λ_z	apparent terminal elimination rate constant

STUDY ADMINISTRATIVE STRUCTURE

The principal investigator (PI) must sign the protocol signature sheet before study participant recruitment may start. Likewise, all protocol amendments must be signed and dated by the PI before coming into effect.

The name and address of the participating center, the investigators, and all required signature documents will be maintained in the trial master file (TMF).

In addition to the PI, there are additional onsite roles that may be performed by other sub-investigators:

- Subject referral to the study
- Review of subject eligibility and medical records
- Clinical evaluations
- Safety assessments
- Injection and imaging
- On-site image analysis

Study personnel not listed in this section are identified in a separate personnel list. This list will be updated as needed. The list of personnel will be available in the center's investigator site file (ISF).

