8.1.3 DAS28 Evaluation

All subjects will be evaluated a single time at screening (Visit 1) for the Disease Activity Score (DAS) 28 ([Prevoo et al, 1995](#)) assessment.

The DAS28 will be calculated from four components: tender joint count (TJC), swollen joint count (SJC), Visual analogue scale (VAS) of the subject's global health, and the laboratory parameter erythrocyte sedimentation rate (ESR). The formula used to calculate the DAS28 score is: $DAS28 = 0.56*\sqrt{(TJC)} + 0.28*\sqrt{(SJC)} + 0.70*LN(ESR) + 0.014*VAS$. See [Appendix 5](#) for details.

A DAS28 score of higher than 5.1 is indicative of high disease activity, whereas a DAS28 below 3.2 indicates low disease activity. A subject is considered to be in remission if they have a DAS28 lower than 2.6

8.1.4 2010 ACR/EULAR Classification Criteria

All subjects will be evaluated at screening using the 2010 ACR/EULAR Classification Criteria as part of eligibility and inclusion.

The 2010 American College of Rheumatology (ACR)/European League Against Rheumatism (EULAR) classification criteria includes four components: number and site of involved joints, serologic abnormality, elevated acute-phase response and symptom duration. See [Appendix 4](#) for details.

A total score of 6 or higher (out of a possible ten) combined with clinical synovitis not better explained by another disease confirms a diagnosis of "definite RA" ([Aletaha et al](#)).

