For subjects enrolled in Groups 1-9: Following completion of the the planar imaging session at 60 minutes, a 3D SPECT or SPECT/CT should be obtained on Joints A and B, followed by a patient break. Following the 180 minute whole body scan, and planar image of the hands, 3D SPECT or SPECT/CT will be repeated for joint A and completed for joint B and/or C in accordance with the prioritization below. No greater than 3 SPECT or SPECT/CT imaging sessions will be obtained after the whole body planar imaging session.

In the event that multiple joints of interest are identified during whole body planar imaging, and the planar image of the hands, the following prioritization will be applied for the selection of joints for SPECT or SPECT/CT imaging. Prioritization for joint selection may be revised after review of the first group of images. Any changes in the prioritization for joint selection will be communicated to investigators prior to the fulfillment of additional doses. Images will be obtained with bilateral joints in the field of view, including both hands, shoulders, elbows, knees.

"Greatest interest" will be defined as the joint of highest Tc99m localization on imaging and as guided by concordance with DAS 28 finding.

1. Joint A will be a the joint of greatest interest as defined above from the planar imaging session. In the event a determination could not be made due to equivalent localization in multiple joints, the hands will be selected as joint A. 3D SPECT or SPECT/CT of Joint A will occur after the 60 and 180 minute whole body scan.
2. Joint B will be the joint of second greatest interest (knee or elbow or shoulder) or the hands if not already imaged as Joint A. 3D SPECT or SPECT/CT of Joint B will follow the 180 minute whole body scan.

3. Joint C would be imaged in the event that Joints A or B were no longer identified as a joint of interest from the 180 minutes whole body imaging. Joint C would be determined by the interest and the discretion of the investigator.

In the event all DAS 28 joints are negative for joint localization on whole body imaging, SPECT/CT may be performed on other areas of localization. A visual representation of the Visit 2, Day 1 imaging procedures for subjects enrolled in Groups 1-9 can be found in [Appendix 2](#).

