It is anticipated that each SPECT or SPECT/CT scan would be acquired (at one bed position) for 25-30 minutes (30 minutes preferred). A break should address the comfort of the patient, encouraging the subject to void, consume fluids or food and to move or rest freely. For areas of low activity uptake, the SPECT scan may need to be increased. It is very important that the subject remain motionless for the duration of the 3D SPECT scan.

The SPECT transverse slices will be reconstructed using the manufacturer's recommended reconstruction algorithms including the recommended attenuation correction.

It is strongly recommended that each site should perform all imaging acquisitions per their camera manufacturer and model parameters and in accordance with their institutional practices for both the whole body scan, planar imaging, as well as the SPECT and SPECT/CT imaging acquisitions.

De-identified DICOM (Digital Imaging Communications in Medicine) copies of all acquired images will be transmitted to Navidea Biopharmaceuticals. The areas of localization will be identified, documented and captured in the eCRFs (electronic case report forms).

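### The plan does not mask the per-joint uptake read to the DAS28 findings it is compared with, so concordance may be inflated

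*Combined protocol and SAP*

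**What the plan says.** - **Image variable (9.3).** The first efficacy variable is a "Nuclear medicine specialist qualitative determination of presence/absence of radiotracer uptake", judged relative to background, at 28 locations per subject. The plan labels this result the gold standard.
- **Clinical comparator (9.3).** "A location/joint would be considered clinically identified as RA positive if it is either swollen or tender as measured by the DAS28 instrument".
- **Concordance (9.3).** It is "the number of joint locations that are clinically RA positive and SPECT illuminated divided by the number of clinically RA positive joints". Only clinically positive joints enter the denominator.
- **Timing (8.1.3).** "All subjects will be evaluated a single time at screening (Visit 1) for the Disease Activity Score (DAS) 28". The result therefore exists before the first image.
- **Use during imaging (8.3, Groups 1-9).** The joint of greatest interest for 3D SPECT or SPECT/CT "will be defined as the joint of highest Tc99m localization on imaging and as guided by concordance with DAS 28 finding".
- **Who reads.** The Study Administrative Structure lists "On-site image analysis" among the roles that sub-investigators may perform, as an item separate from clinical evaluations. Section 8.3 adds, in the passive, "The areas of localization will be identified, documented and captured in the eCRFs". It also sends de-identified DICOM copies of all images to the sponsor. No place describes a masked, independent or central read.
- **Analysis (9.5.3).** Concordance is computed descriptively, with no test or threshold. Other efficacy analyses are left to a SAP.

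**The concern.** The uptake call is a visual judgement against background, and some joints will be borderline. Its comparator is already on file, and section 8.3 asks for localization to be weighed together with that comparator while the session is under way. Sections 7.2.2.2 and 8.2 point the same way: placement of the IV line depends on whether both elbows are primary RA imaging sites, so some clinical joint information reaches nuclear medicine before the first scan.

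A reader who knows that a joint is tender may call a faint signal positive, and one who knows that it is not may call the same signal negative. The first raises concordance and the RA-identified localization rate. The second lowers the rate of localization outside RA-positive joints. Both make the agent look better. Concordance with clinical symptoms is a named secondary objective (2.2), and the localization rates tabulated by dose group and time point come from the same read.

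**Working it through.** The plan states no expected concordance, sample size or power for this endpoint, so there is no figure to reproduce. The check has two parts.

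**1. What the text establishes about the reader**

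| Question | Answer in the plan |
|---|---|
| Is the call subjective? | Yes: qualitative, relative to background (9.3) |
| Does DAS28 exist before imaging? | Yes: done at screening (8.1.3) |
| Is DAS28 used in the session? | Yes, for choosing 3D joints in Groups 1-9 (8.3) |
| Is the person who chooses those joints the specialist of 9.3? | Not stated |
| Is the specialist masked to DAS28? | Not stated |
| Which images feed the 28-joint call? | SPECT imaging results (9.3); planar or 3D not stated |

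On the last row: 8.3 allows three joint sites at most (A, B, C) and names four bilateral ones (hands, shoulders, elbows, knees). If the wrists fall in the hands view, the most that 3D imaging can cover is 22 + 2 + 2 = 26 of the 28 joints. A call on all 28 therefore needs the planar images for at least some of them.

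**2. How large the effect could be (assumed inputs)**

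Let r be concordance under a masked read, and u the share of clinically positive joints in which the reader follows DAS28 whatever the image shows. Then

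observed = r(1 − u) + u = r + u(1 − r).

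With r = 0.70:
- u = 0.05: 0.665 + 0.05 = 0.715
- u = 0.10: 0.63 + 0.10 = 0.73
- u = 0.20: 0.56 + 0.20 = 0.76

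If u applies only to equivocal joints, these are a share e of the clinically positive joints, and their lit rate is also r, then observed = r + e·u(1 − r). With e = 0.20:
- u = 0.05: 0.70 + 0.20 × 0.05 × 0.30 = 0.703
- u = 0.20: 0.70 + 0.20 × 0.20 × 0.30 = 0.712

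The first formula over a wider range:

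| r | u = 0 | u = 0.10 | u = 0.25 | u = 0.50 |
|---|---|---|---|---|
| 0.40 | 0.40 | 0.46 | 0.55 | 0.70 |
| 0.60 | 0.60 | 0.64 | 0.70 | 0.80 |
| 0.80 | 0.80 | 0.82 | 0.85 | 0.90 |

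In clinically negative joints the same behaviour gives q(1 − u), where q is the masked lit rate. With q assumed to be 0.30, u = 0.05, 0.10 and 0.20 give 0.285, 0.27 and 0.24. The endpoint itself is per subject (at least one such joint lit), so its shift also depends on how many negative joints each subject has. The direction is downward.

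With u = 0, whether through masking or because the reader is not influenced, nothing changes.

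**The case against.** The strongest reply is that the plan nowhere says that the specialist sees DAS28. A reader might infer from 8.3, the on-site image role and the open-label design that the specialist works with the DAS28 findings in hand and that concordance is therefore biased. The documents do not support that. Section 8.3 governs which joints are scanned in 3D and does not name the chooser as the reader of 9.3. Image analysis and clinical evaluations are listed as separate roles. Open label describes treatment assignment, not image reading. This part of the objection stands, and the point is limited to a risk.

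Three further objections also stand:
- **RA or control status** cannot distort concordance in the primary efficacy set. The ITD population is Groups 1-9, and all of them have RA. Status matters only where images from Groups 10-11 are read, for instance for the comparison with controls in 2.2.
- **Repair is possible.** A reader might infer that the damage could never be undone. The stored DICOM images allow a masked re-read, and the per-joint quantitative intensity does not rest on the positive/negative call.
- **Stakes are moderate.** The primary endpoint is safety, and concordance is a descriptive secondary endpoint with no decision rule.

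A last objection concerns the remedy. If one person reads at 60 minutes and is then given DAS28 to choose the 3D joints, that person is unmasked for the 180-minute read. The session is also tight. With two 3D scans after the first planar session, the durations in 8.3 (hands view counted once) give 60 + 25 + 5 + 2 × 25 = 140 to 60 + 30 + 7 + 2 × 30 = 157 minutes, and the second window opens at 180 − 15 = 165. This is right, and it is why the fix separates the two tasks instead of only ordering them.

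What the objections do not remove is that the plan brings the comparator into the imaging session and has no rule that keeps it from the reader. De-identifying images does not by itself withhold the joint map.

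**Conclusion.** The point holds as a gap in control. The per-joint read is subjective, its comparator is available beforehand and is used during the session, and the plan does not mask the reader to it. Unless the endpoint read is masked, concordance may be inflated and localization in clinically negative joints may be lowered.

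The documents fix neither the existence nor the size of the effect. From a masked value of 70%, the illustrative rise is 1.5 to 6 points if DAS28 sways 5-20% of all clinically positive joints. It is 0.3 to 1.2 points if it sways that share of equivocal joints only and 20% are equivocal. The values of r, u and e are all assumptions.

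One limit: 9.5.3 refers further efficacy detail to a SAP, and the document holds no separate SAP text. A masking rule written there would settle the matter. This is a cheap improvement to a secondary objective and does not touch the primary endpoint.

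**What to change.** Amend 8.3 and 9.3, with matching eCRF wording, to state:

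1. The nuclear medicine specialist records and locks the presence/absence call for all 28 joints, at both 60 and 180 minutes, without the DAS28 joint map or dose group. Where Groups 10-11 are read, RA/control status is withheld too.
2. Existing site staff other than that reader, for example the investigator who holds the DAS28, make the DAS28-guided choice of joints for 3D SPECT or SPECT/CT.
3. Alternatively, the specialist makes the endpoint read afterwards from the de-identified DICOM copies, provided that this specialist took no part in choosing joints.
4. Which images, planar or 3D SPECT, the 28-joint call uses. If planar, lock the calls before the reader sees which joints were taken to 3D, since that choice itself hints at the DAS28 result.

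The cost is a division of tasks at the imaging session, or a slightly later read, plus protocol and eCRF wording. No additional scan, visit or subject is needed, and no extra reader as long as the specialist is kept out of joint selection.

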9.5.3 Analysis of Efficacy Variables

Per subject localization rates and percentage will be calculated by imaging time point by dose group and overall.

Per joint location localization rates and percentages will be calculated by time point by dose group and overall.

Per location concordance of clinical diagnosis to nuclear medicine specialist illumination indication will be computed across all RA positive sites of all subjects at all time points.

Localization intensities will be summarized by descriptive statistics (mean, median, standard deviation, minimum, maximum and range) by joint location at each time point.

Other efficacy analyses will be described in the Statistical Analysis Plan (SAP) for the study.

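### Section 9.3 names the tracer read as the gold standard, while its own formulas take DAS28 clinical status as the reference, and Section 9.5.3 does not say which meaning of RA positive applies

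*Combined protocol and SAP*

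**What the plan says.** Section 9.3 (Efficacy Variables) lists the nuclear medicine specialist's call of uptake present or absent at each DAS28 joint, and that read is "deemed the “gold standard” result, 28 joint locations per subject". It then gives two ways for a joint to be RA positive:

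- Clinical: "A location/joint would be considered clinically identified as RA positive if it is either swollen or tender as measured by the DAS28 instrument".
- Tracer: uptake "as determined by the nuclear medicine specialist at a location would indicate the location is RA positive".

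The endpoint formulas in Section 9.3 use the clinical definition. Concordance counts the joints that are "clinically RA positive and SPECT illuminated divided by the number of clinically RA positive joints". The rate of localization outside RA-positive joints is "the illumination of at least one joint location relative to background that is clinically RA negative in a subject divided by the number of subjects". The endpoint list agrees with this, because it refers concordance to areas of active RA defined by clinical symptoms, and so does the secondary objective in Section 2.2.

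Section 9.5.3 describes the analysis differently. It computes concordance of the clinical diagnosis to the specialist's read "across all RA positive sites of all subjects", at all time points, without the word clinically. The Data Analyses entry in the synopsis has the same wording.

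**The concern.** A gold standard is the result against which others are judged. Tilmanocept imaging is the test under study: Section 3.2 sets out to evaluate it as an imaging agent in subjects with known active RA. If its read is also the standard, the comparison is circular.

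The label and the formulas assign opposite roles to the image and the joint examination. Section 9.5.3 does not settle the matter: its denominator is unqualified, and it compares the clinical diagnosis to the image, a direction that fits the gold-standard label better than the Section 9.3 formula.

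Two things are at stake. The first is which joints form the concordance denominator. The second is interpretation. If the label governs, an unlit swollen joint can be put down to an error of the examination, and a lit normal joint can be presented as disease that the examination missed.

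**Working it through.** The plan states no figure for this point, so there is none to reproduce. The check compares the definitions and then applies each reading to an assumed table.

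**Notation.** At joint level, a = clinical+/SPECT+, b = clinical+/SPECT-, c = clinical-/SPECT+ and d = clinical-/SPECT-.

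**What each place implies.**

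- Section 9.3, concordance formula: a/(a+b). The reference is clinical.
- Section 9.3, gold-standard label: the reference is SPECT. Read as a proportion of lit joints, that is a/(a+c). The plan does not write this formula.
- Section 9.3, both definitions of RA positive applied together: the denominator is a+b+c. The plan does not write this formula either.
- Section 9.5.3 and the synopsis: RA positive sites, with the definition left open.

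**Hypothetical illustration.** The documents give no joint counts. Take 27 subjects (nine groups of three, Table 1) with 28 joints each, so 27 × 28 = 756 joints, and assume a = 200, b = 100, c = 50, d = 406.

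- Clinical reference: 200/(200+100) = 66.7%.
- SPECT reference: 200/(200+50) = 80.0%.
- RA positive by either definition, positive on both: 200/(200+100+50) = 57.1%.
- RA positive by either definition, illuminated: 250/350 = 71.4%.
- RA positive by uptake alone, illuminated: 250/250 = 100%, by construction.

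Only the first of these is a formula that the plan states. The others show what the open wording would allow.

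**Does discordance count under the Section 9.3 formulas?**

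- *Unlit, clinically positive joints.* Move 100 joints from a to b. Concordance falls from 200/300 = 66.7% to 100/300 = 33.3%, so these joints count.
- *Lit, clinically negative joints.* Move 100 joints from d to c, so that c rises from 50 to 150 and d falls from 406 to 306. Concordance stays at 200/300 = 66.7%. The per-joint RA-identified localization rate, which divides by all joints, stays at 200/756 = 26.5%. The share of clinically negative joints that light up goes from 50/456 = 11.0% to 150/456 = 32.9%. Equivalently, joint-level specificity goes from 89.0% to 67.1%. Neither quantity is a listed endpoint.

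The lit, clinically negative joints enter only the per-subject off-target rate. A subject with one such joint counts there the same as a subject with many.

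**The case against.** The strongest reply is that the formulas settle the matter. The objective, the endpoint list and the concordance definition all refer to clinical disease, and an explicit formula should govern an abbreviated restatement. On that view the defect is one word missing from Section 9.5.3 and the synopsis. This has force: a careful programmer would probably use the clinical denominator. It does not remove the gold-standard label or the uptake sentence, which stand in the same section as the formulas and contradict them.

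A reader might infer that no result could count against the tracer, or that the off-target endpoint is empty because every lit joint is RA positive. The documents do not support either inference. Every unlit swollen or tender joint lowers concordance as defined, and the off-target rate is expressly defined on clinically RA negative joints. Both inferences require the general uptake sentence to override explicit endpoint definitions.

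It can also be said that DAS28 is an imperfect reference, since Section 1.1 argues that macrophage infiltration can precede clinical signs. That is a fair scientific argument for examining lit, clinically negative joints. It is not a reason to declare them positive in advance in a study that measures agreement with clinical findings.

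The concern about healthy controls has limited reach. The primary efficacy set (ITD) is Groups 1-9, all with RA. Controls could enter efficacy analyses only through the per-protocol set, which Section 9.5.1 draws from all safety subjects.

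**Conclusion.** The point holds as an inconsistency in the reference standard. Section 9.3 states two conflicting references, one of them the test itself, and Section 9.5.3 and the synopsis leave the concordance denominator open. Separately, even with the clinical reference, lit clinically negative joints never reduce concordance and have no joint-level rate.

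The size cannot be estimated from the documents. In the assumed table, the overlap proportion ranges from 57.1% to 80.0% depending on the reading. That range is a hypothetical illustration that includes formulas the plan does not state. The contradiction does not depend on the assumed counts.

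The consequence is moderate. These are secondary endpoints, summarised descriptively, with no test, threshold or sample size resting on them, and the primary endpoint is safety. It is still worth correcting, because concordance with clinical findings is a stated secondary objective.

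**What to change.** 1. In Section 9.3, delete the gold-standard label and the sentence that uptake indicates an RA positive location.
2. State once that DAS28 swollen or tender status is the reference for RA positive in all of these endpoints.
3. Write clinically RA positive in Section 9.5.3 and in the Data Analyses entry of the synopsis, and carry the same wording into the SAP.
4. Keep the Section 9.3 concordance formula, a/(a+b).
5. Add the four joint-level counts (a, b, c, d) by time point, and report c/(c+d), the proportion of clinically negative joints that light up, beside concordance. Keep the per-subject off-target rate.

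The cost is wording and one extra table. Section 9.3 already provides for both calls at 28 joints per subject, and Section 9.5.5 already requires both for a joint to be analysed, so no new data are needed. The downside for the sponsor is that the reported agreement may look less favourable.
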